As an additional safeguard, the first three patients enrolled on study will be observed for 30 days following treatment completion of the third patient before enrollment is continued (fourth patient). If two or three of the first three study patients have grade 3 or higher GI/GU toxicity within 30 days of treatment completion, enrollment will be suspended pending DSMC review. If none or one of the first three patients enrolled on study have grade 3 or higher GI/GU toxicity

within 30 days of treatment completion, enrollment will continue without restriction on the interval between successive enrollments.

Posterior probabilities used to derive the preceding table are calculated under a prior beta distribution with parameters $\beta_1 = 0.2$ and $\beta_2 = 1.8$, which corresponds to an expected rate of 15% based on prior information roughly equivalent to having studied 2 patients^{96,97}. Furthermore, this prior distribution assigns a small a priori chance (32%) to the possibility that the true rate of unacceptable toxicity is 15% or greater.

Table 3. Stopping Rules For Lack of Feasibility

Number of Patients ineligible For LEAD	Total Patients enrolled and completed CT simulation	Observed LEAD ineligibility rate
2	3	67%
3	4 to 6	≥50% (3 of 6)
4	7 to 10	≥40% (4 of 10)
5	11 to 13	≥38% (5 of 13)
6	14 to 17	≥35% (6 of 17)
9	18 to 25	≥35% (9 of 25)

Stopping rules for lack of feasibility

Similarly, for purposes of monitoring the feasibility of delivering LEAD RT, we consider the proportion of patients enrolled on study for whom it is not possible to deliver LEAD RT as determined from CT/MRI simulation and planning, referred to as the *LEAD ineligibility rate*. The LEAD treatment will not be delivered if the summed dose of LEAD and conventional treatment to critical structures exceeds tolerance. Early stopping due to infeasibility of the proposed study treatment will be considered if there is evidence that the rate of LEAD ineligibility exceeds

20%. Specifically, we suggest as a guideline for early termination a posterior probability of 90% or higher that the rate of unacceptable toxicity exceeds 20%. **Table 3** shows specific instances where this guideline is met, thus suggesting early termination due to early evidence of LEAD infeasibility.

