Posterior probabilities used to derive the preceding table are calculated under a prior beta distribution with parameters $\beta_1 = 0.4$ and $\beta_2 = 1.6$, which corresponds to an expected rate of 20% based on prior information roughly equivalent to having studied 2 patients. Furthermore, this prior distribution assigns a small a priori chance (36%) to the possibility that the true rate of unacceptable toxicity is 20% or greater.

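### The last row of the feasibility stopping table (9 of 18 to 25) does not follow from its own 90% rule, which is met at 7 (n = 18–21) and 8 (n = 22–25)

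*Combined protocol and SAP*

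**What the plan says.** The feasibility part of Section 14.4 defines a LEAD ineligibility rate: the proportion of enrolled patients to whom LEAD RT cannot be delivered, as judged at simulation and planning. It then states: "Early stopping due to infeasibility of the proposed study treatment will be considered if there is evidence that the rate of LEAD ineligibility exceeds" 20%. The numerical criterion follows: "a posterior probability of 90% or higher that the rate of unacceptable toxicity exceeds 20" per cent. Table 3 is tied to that criterion, since it "shows specific instances where this guideline is met, thus suggesting early termination due to early evidence of LEAD infeasibility".

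Table 3 lists these counts of ineligible patients: 2 of 3, 3 of 4–6, 4 of 7–10, 5 of 11–13, 6 of 14–17 and 9 of 18–25. The posterior probabilities behind it are said to come from a beta prior with parameters 0.4 and 1.6, "which corresponds to an expected rate of 20% based on prior information roughly equivalent to having studied 2 patients". The text adds that "this prior distribution assigns a small a priori chance (36%) to the possibility that the true rate of unacceptable toxicity is 20% or greater".

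**The concern.** The required count rises by one from row to row, reaching 6 at n = 17, and then jumps to 9 at n = 18. A fixed posterior criterion cannot produce such a jump, because one more patient changes the minimum count by at most one. The rows above are minimum counts, so the Data and Safety Monitoring Committee (DSMC) would naturally read 9 as the boundary. It would then see no signal at 7 or 8 ineligible patients, even where the written criterion is met. Feasibility is part of the primary objective (Section 2.1), and Section 14.1 makes enrolment subject to early stopping for it. The last row covers 8 of the 25 planned patients.

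A smaller matter is that the criterion sentence and the prior sentence both name a toxicity rate, although the paragraph monitors LEAD ineligibility.

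**Working it through.** **Inputs (all from Section 14.4).** Prior Beta(0.4, 1.6); threshold rate 20%; posterior cut-off 90%; Table 3 counts.

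**Prior check.** Mean = 0.4 / (0.4 + 1.6) = 0.20. P(rate > 0.20) = 0.361. Both agree with the stated 20% and 36%, so the prior is as printed.

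**Rule.** With x ineligible among n, the posterior is Beta(0.4 + x, 1.6 + n − x). The boundary at n is the smallest x with P(rate > 0.20) ≥ 0.90.

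**Rows that reproduce as minimum counts.**
- 2 of 3: 0.907
- 3 of 4–6: 0.973 to 0.914
- 4 of 7–9: 0.970 to 0.925
- 5 of 11–13: 0.956 to 0.913
- 6 of 14–17: 0.961 to 0.907

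The one exception is 4 of 10, at 0.895. It reaches 90% only by rounding; strictly, n = 10 needs 5 (0.971).

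**The last row.**

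| n | Minimum count under the rule | Posterior | Posterior with one fewer | Posterior at the printed 9 |
|---|---|---|---|---|
| 18 | 7 | 0.955 | 0.883 | 0.996 |
| 19 | 7 | 0.940 | 0.856 | 0.994 |
| 20 | 7 | 0.923 | 0.826 | 0.991 |
| 21 | 7 | 0.904 | 0.794 | 0.987 |
| 22 | 8 | 0.950 | 0.882 | 0.982 |
| 23 | 8 | 0.937 | 0.858 | 0.976 |
| 24 | 8 | 0.921 | 0.831 | 0.968 |
| 25 | 8 | 0.903 | 0.802 | 0.959 |

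The table therefore flags 6 of 17 (35%, posterior 0.907) but not 8 of 18 (44%, 0.986) or 8 of 20 (40%, 0.972).

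**Could another rule give 9?** Cut-offs of 80, 85, 95, 97.5 and 99%, a threshold of 25%, and five other priors were tried, one change at a time: Beta(0.2, 1.8), (0.3, 1.7), (0.6, 1.4), (0.5, 0.5) and (1, 1). None gives 9 throughout n = 18–25 together with the earlier rows. The row also prints 9 of 25 as its observed rate, so the 9 is not a text-extraction fault.

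**Effect on monitoring.** Exact recursion, assuming a look after each patient from n = 3. The corrected columns change the last row only.

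| True ineligibility | Flag by n = 25: table | Flag by n = 25: corrected | Open after 17 | Flag in 18–25 if open: table | Flag in 18–25 if open: corrected |
|---|---|---|---|---|---|
| 20% | 24.0% | 26.8% | 76.6% | 0.8% | 4.4% |
| 30% | 58.0% | 64.5% | 45.2% | 7.1% | 21.5% |
| 40% | 86.1% | 90.6% | 18.2% | 23.8% | 48.3% |

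If n = 10 is also moved to a count of 5, the overall figures become 25.9%, 63.8% and 90.4%.

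Under this schedule a trial still open after 17 patients has at most 5 ineligible. The printed 9 then cannot be reached before n = 21 (5 + 4), so the last row cannot act at n = 18–20.

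**The case against.** The strongest reply is that the guideline is advisory and the table is not the rule. The prior and cut-off are printed, the DSMC can compute the posterior at any n, and the text offers the table as instances. Nine of 18–25 does meet the criterion, so the row causes no false stop. This is true, but it does not reconcile the table with the rule. The table is titled as stopping rules and its other rows are minimum counts (4 of 10 by rounding), so a committee working from it would take 9 as the boundary.

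Second, with a look after every patient, 7 or 8 of 18 cannot occur in a trial still open, and the discrepancy starts at n = 19. That is correct for that schedule. Section 14.4 allows review at any stage without fixing the looks in advance, and Appendix III speaks of periodic review, so those states can arise in practice. The probabilities above would then no longer apply exactly.

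Third, the overall effect is modest. The large contrasts apply only to trials open after 17 patients. With n = 10 also changed, expected enrolment is practically the same as with the printed table (15.22 against 15.21 at 30%; 9.94 against 9.95 at 40%). The final feasibility estimate in Section 14.2 does not use Table 3, and patients found ineligible are not given LEAD RT. All of this stands and limits the consequence, but not the error.

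Fourth, the toxicity wording is an editorial carry-over. The definition, the sentence before it and the table title make the meaning clear. Likewise 4 of 10 is a rounding matter that errs towards earlier review. Both are minor.

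**Conclusion.** The concern holds. Under the stated prior and criterion the boundary is 7 for n = 18–21 and 8 for n = 22–25, and the printed 9 contradicts the rule it is meant to display. These counts are exact and depend on no assumption about the timing of looks.

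The cost to monitoring does depend on one, namely a look after every patient from n = 3. On that basis the overall chance of flagging infeasibility falls short by 64.5 − 58.0 = 6.5 percentage points at a true rate of 30%, and by 90.6 − 86.1 = 4.5 points at 40%. Among trials still open after 17 patients, the printed row loses about two thirds of the chance of a late flag at 30% and about half at 40%. The toxicity wording and the 4-of-10 cell are secondary, and the conclusion does not rest on them.

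**What to change.** - Replace the last row of Table 3 with two rows: 7 for 18 to 21 (lowest observed rate 7/21 = 33%) and 8 for 22 to 25 (8/25 = 32%).
- For n = 10, either use 4 for 7–9 and 5 for 10–13, or keep the row and note that 4 of 10 gives 89.5%.
- In the criterion sentence and the prior sentence, name the LEAD ineligibility rate instead of a toxicity rate.
- If 9 was intended, state the different criterion that produces it.

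The cost is one table and two phrases, with no change to sample size or treatment. The downside is a few more reviews when the true ineligibility rate is exactly 20%: 26.8% against 24.0% with only the last row corrected, or 25.9% if n = 10 is changed as well.

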14.5 Reporting and Exclusions
N/A

15.0 INVESTIGATOR’S RESPONSIBILITIES

15.1 Investigator Responsibility/Performance

The investigator will ensure that this study is conducted in accordance with all regulations governing the protection of human subjects.

The investigator will ensure that all work and services described in or associated with this protocol will be conducted in accordance with the investigational plan, applicable regulations, and the highest standards of medical and clinical research practice.

15.2 Confidentiality

The investigator must ensure that each subject’s anonymity will be maintained and each subject’s identity will be protected from unauthorized parties. A number will be assigned to each subject upon study entry and the number and the subject’s initials will be used to identify the subject for the duration of the study. The investigator will maintain all documents related to this study in strict confidence.

15.3 Informed Consent and Permission to Use Protected Health Information

It is the responsibility of the investigator to obtain written informed consent from each subject participating in this study after adequate explanation, in lay language, of the methods, objectives, anticipated benefits, and potential hazards of the study. The investigator must also explain that the subject is completely free to refuse to enter the study or to discontinue participation at any time (for any reason) and receive alternative conventional therapy as indicated. Prior to study participation, each subject will sign an IRB approved informed consent form and receive a copy of same (and information leaflet, if appropriate). For subjects not qualified or able to give legal consent, consent must be obtained from a parent, legal guardian, or custodian.

The investigator or designee **must** explain to the subject before enrollment into the study that for evaluation of study results, the subject's protected health information obtained during the study may be shared with the study sponsor, regulatory agencies, and the IRB. It is the investigator's (or designee's) responsibility to obtain permission to use protected health information per HIPAA from each subject, or if appropriate, the subjects' parent or legal guardian.

15.4 Source Documentation and Investigator Files

The research team will maintain adequate and accurate records to fully document the conduct of the study and to ensure that study data can be subsequently verified. These documents will be classified into two separate categories: (1) investigator study file and (2) subject clinical source documents that corroborate data collected on any CRFs. Subject clinical source documents would include hospital/clinic patient records; physician's and nurse's notes; original laboratory, radiology, pathology, and Quality of Life surveys; signed informed consent forms. When the CRF or any form is used as the source document, this must be clearly stated in the investigator study file.

At a minimum the following source documents will be collected:

- Medical history/physical condition and diagnosis of the subject before involvement in the study sufficient to verify protocol entry criteria
- Study number, assigned subject number, and verification that written informed consent was obtained (each recorded in dated and signed notes on the day of entry into the study)
- Progress notes for each subject visit, including treatment toxicity
- Documentation of treatment
- Laboratory test results
- Adverse events (action taken and resolution)
- Condition and response of subject upon completion of or early termination from the study
- Quality of Life Surveys
- Pre-treatment multiparametric-MRI tumor size and location generated by the in-house developed software and/or the investigator's contours.
- Radiation treatment Dose Volume Histogram analysis results

15.5 Recording and Processing of Data

If using hard copies of CRFs, study center personnel will complete individual CRFs in black ink. All corrections to entered data will be made by drawing a single line through the information to be corrected without obscuring it. **All corrections will be initialed**, dated and explained, if necessary. **Do not use "white-out" or obscuring correction tape.** A CRF is required for every patient who received any amount of study treatment. The investigator will

ensure that the CRFs are accurate, complete, legible and timely. Separate source records are required to support all CRF entries.

15.6 Non-Protocol Research

No investigative procedures other than those described in this protocol will be undertaken on the enrolled subjects without the agreement of the IRB.

15.7 Ethics

The investigator agrees to conduct the study in compliance with the protocol, current good clinical practices, and all applicable (local, FDA) regulatory guidelines and standard of ethics.

15.8 Essential documents for the conduct of a clinical trial

Essential documents are those documents with individually and collectively permit evaluation of the conduct of a trial and the quality of the data produced.

The following documents should be on file:

- 1572 (for studies involving IND drugs or devices)
- CV's and license of all investigators
- IRB documentation/correspondance
- Documentation of IRB certification

APPENDIX I
STUDY CALENDAR

Assessment	Prior to RT	24 hr Post-LEAD RT	Weekly during RT	Follow-up				
				During last week of RT	6 Weeks	3 Mo	Every 6 months thereafter up to 5.25 years post-RT	Other
History & Physical Exam*	X		X	X	X	X	X	
Multiparametric MRI of prostate/pelvis ^a	X					X		At 9 mo, and within 2 mo of 2 yr prostate biopsy
Bone Scan or PET Bone Scan ^b	X							As needed
Prostate Biopsy ^c	X							2 – 2.5 years post completion of all therapy
CT and MRI simulation	X							As needed
PSA ^a	X				X	X	X	
Serum-Testosterone ^d	X			X	X	X		At 9 months after RT
BUN and creatinine						X		At 9 months and within 2 mo of 2 yr prostate biopsy
Liver function tests ^a	X			X	X	X		
Complete blood cell counts ^a	X			X		X		
Lipid Profile ^a	X	X		X	X	X		At 9 months and within 2 mo of 2 yr prostate biopsy
EPIC-SF12 ^e	X			X	X	X		At 9 months, 15 mo and yearly to 5.25 years
MAX-PC ^e	X			X	X	X		At 9 months, 15 mo and yearly to 5.25 years
IPSS ^f	X			X	X	X	X	At each follow-up visit
Start of ADT ^g	X							
Plasma and serum, and urine collection for research ^h	X	X		X	X	X		At 9 months and within 2 mo of 2 yr prostate biopsy

*Toxicity and performance status (Zubrod score) will be assessed at each scheduled history and physical exam visit. Interval history will be obtained during following RT at these visits. On-treatment and follow-up physical exams are focused per routine.

- ^aObtained \leq 3 months of signed consent and complete blood count and liver function tests (LFTS). If ADT is not administered, only pretreatment and 3 month LFTs are required. Lipid panels are preferred to be fasting (not required).
- ^bObtained \leq 4 months of enrollment if PSA >15 ng/mL or Gleason score $8 \geq$ disease. A questionable bone scan is acceptable if other imaging is negative for metastasis. For all others, to be obtained at the discretion of the treating physician.
- ^c The initial biopsy will be carried out during fiducial markers placement (if patient opts to have biopsy), within 4 weeks after enrollment (registration). In follow-up, prostate biopsy will be obtained at first sign of local failure or a rising PSA, or at 2-2.5 years after treatment (after radiotherapy or androgen deprivation – whichever is longer) if no evidence of failure.
- ^dSerum testosterone will be drawn as part of routine workup ≤ 4 months before signed consent or after enrollment but prior to the first radiation treatment and must be within 40% of normal assay limits, defined as $x=0.4$ *lower assay limit and $x=0.4$ *upper assay limit + upper assay limit. Patients who have been started on ADT prior to signing consent are not required to have a serum testosterone at this level; but, a serum testosterone prior to fiducial marker placement is recommended. Serum testosterone will be drawn at the end of RT, 6 weeks, 3 months, and 9 months after radiotherapy. If testosterone remains abnormally low, tests will continue to be done at each follow-up visit.
- ^eAfter enrollment (registration) and prior to fiducial marker placement.
- ^f International Prostate Symptom Score will be administered pretreatment, at the end of treatment and at each follow-up visit.
- ^gAndrogen deprivation therapy (ADT) for applicable patients: ADT is recommended to be initiated after fiducial marker placement. Anti-androgen treatment is recommended to begin 1-14 days before LHRH agonist start. ADT may occur up to 2 months prior the signing of consent (timing is relative to LHRH agonist injection). If not started prior to consent, ADT is recommended to start after fiducial marker placement and prior to radiotherapy start.
- ^hAfter enrollment and prior to fiducial marker placement 2-4 tubes of blood and 50 mL of urine will be collected, as described in Sections 4.11, 4.12 and 5.0 for research studies.

Note: Measurements and visits during treatment should occur \pm 3 days; measurements and visits during follow-up should occur \pm 2 weeks up to the 3 month visit and \pm 4 weeks for subsequent measurements/visits, with the exception of the post-LEAD RT lipids and blood & urine collection for research, which is 24 hr \pm 12 hr.

APPENDIX II

NATIONAL CANCER INSTITUTE (NCI) COMMON TOXICITY CRITERIA (CTC)

The NCI CTCAE criteria may be viewed on-line at the following NCI web site:

<http://ctep.cancer.gov/reporting/ctc.html>

APPENDIX III

DATA AND SAFETY MONITORING PLAN

The Sylvester Comprehensive Cancer Center (SCCC) Data and Safety Monitoring Committee (DSMC) will monitor this clinical trial according to the Cancer Center's DSM Plan. In its oversight capacity, the DSMC bears responsibility for suspending or terminating this study.

DSMC oversight of the conduct of this trial includes ongoing review of accrual and adverse event data, and periodic review of toxicity and feasibility. The guidelines appearing in Section 11.0 are offered for DSMC consideration in assessing adverse events. In addition, the DSMC will review reports from all audits, site visits, or study reviews pertaining to this clinical trial and take appropriate action.

The SCCC DSM Plan to which this study is subject can be found at:

[http://10.64.1.160/eForm///Clinical%20Research%20Services/Data%20and%20Safety%20Monitoring%20Committee%20\(DSMC\)/DSMC%20Plan_120407.pdf](http://10.64.1.160/eForm///Clinical%20Research%20Services/Data%20and%20Safety%20Monitoring%20Committee%20(DSMC)/DSMC%20Plan_120407.pdf)

APPENDIX IV
DATA SUBMISSION SCHEDULE

FORM	TO BE COMPLETED
BASELINE	
Eligibility Checklist	Prior to registration
SCCC Protocol Enrollment Form	
Consent Forms Signed/dated	
On-study Form	Within 30 days of registration
DURING PROTOCOL THERAPY	
	Due every week for phase I studies, every cycle for phase II-IV studies
AFTER PROTOCOL THERAPY	
Off Treatment Form	Within 14 days of discontinuation/completion of protocol therapy
FOLLOW-UP SCHEDULE (for studies with long term follow-up)	
Follow-up Form	At during the last week of RT, and after RT at 6 weeks, 3 months, and every 6 months to 5.25 yr after RT.
Progression/Relapse	Within 4 weeks of knowledge of progression/relapse
Notice of Death Form	Within 4 weeks of knowledge of death
Subsequent Malignancy	Within 4 weeks of knowledge of another malignancy

APPENDIX V
ADDITIONAL ITEMS

For the safety of our patients, please refrain from using the following prohibited and/or misleading abbreviations in the treatment and dose modification sections of the protocol.

Abbreviation	Definition	Term to Use
U	For unit	Unit
IU	For international unit	International unit
Pharmacy abbreviations	Example, qd for daily	Daily
1.0 mg	Trailing zero	1 mg
.1 mg	Lack of leading zero	0.1 mg
Drug name abbreviations	Example, MS for morphine sulfate	Write out drug name
µg	microgram	mcg
d/c	Discharge	Discharge
Cc	cubic centimeter	ml (milliliter)
>	Greater than	Write out meaning
<	Less than	Write out meaning

APPENDIX VI PERFORMANCE SCALES

ECOG / WHO / Zubrod	Karnofsky	Activity
Zubrod 0	Karnofsky 90-100	Normally Active
Zubrod 1	Karnofsky 70-80	Symptoms but ambulatory where strenuous physical activity is restricted
Zubrod 2	Karnofsky 50-60	In bed less than 50 percent of the time. Capable of all self-care
Zubrod 3	Karnofsky 30-40	In bed more than 50 percent of the time. Capable of only limited self-care.
Zubrod 4	Karnofsky 10-20	Completely disabled and bedridden.
Death		

APPENDIX VII

The Modified 18-Item Memorial Anxiety Scale for Prostate Cancer

We would like to better understand how patients cope with aspects of their treatment for prostate cancer and the medical tests frequently involved in their care.

Below is a list of comments made by men about prostate cancer. Please indicate by circling the number next to each item how frequently these comments were true for you *during the past week* using the following scale: not at all=0, rarely=1, sometimes=2, often = 3.

1. Any reference to prostate cancer brought up strong feelings in me. ____
2. Even though it's a good idea, I found that getting a PSA test scared me. ____
3. Whenever I heard about a friend or public figure with prostate cancer, I got more anxious about my having prostate cancer. ____
4. When I thought about having a PSA test, I got more anxious about my having prostate cancer. ____
5. Other things kept making me think about prostate cancer. ____
6. I felt kind of numb when I thought about prostate cancer. ____
7. I thought about prostate cancer even though I didn't mean to. ____
8. I had a lot of feelings about prostate cancer, but I didn't want to deal with them. ____
9. I had more trouble falling asleep because I couldn't get thoughts of prostate cancer out of my mind. ____
10. I was afraid that the results from my PSA test would show that my disease was getting worse. ____
11. Just hearing the words "prostate cancer" scared me. ____

For the next three questions, please indicate how frequently these situations have *EVER*

been true for you using the following scale: not at all=0, rarely=1, sometimes=2, often = 3.

12. I have been so anxious about my PSA test that I have thought about delaying it. ____

13. I have been so worried about my PSA test result that I have thought about asking my doctor to repeat it. ____

14. I have been so concerned about my PSA test result that I have thought about having the test repeated at another lab to make sure they were accurate. ____

Listed below are a number of statements concerning a person's beliefs about their own health.

In thinking about the *past week*, please indicate how much you agree or disagree with each statement: strongly agree =0, agree =1, disagree =2, or strongly disagree =3. Please circle the number of your answer.

15. Because cancer is unpredictable, I feel I cannot plan for the future. ____

16. My fear of having my cancer getting worse gets in the way of my enjoying life. ____

17. I am afraid of my cancer getting worse. ____

18. I am more nervous since I was diagnosed with prostate cancer. ____

